5.1.1.4 Combination Dosing

On days where both gilteritinib and atezolizumab are dosed, gilteritinib is to be taken first, then atezolizumab second, when subject is in the clinic. It should be noted that trough pharmacokinetic samples should be collected within 1 hour prior to gilteritinib dosing, and time points for blood samples collected for FLT3 and AXL (cycle 1/day 1 – pre-dose and post-dose at 2 hours, between 4 to 6 hours and 24 hours) are relative to gilteritinib dose administration. If in the opinion of the investigator the subject no longer receives clinical benefit from or experiences unacceptable toxicity that is related to either gilteritinib or atezolizumab, then the subject may discontinue either gilteritinib or atezolizumab and continue to receive the other agent.

5.1.2 Reduction in Dose of the Study Drug(s)

5.1.2.1 Gilteritinib Dose Reduction

Gilteritinib dose cannot be reduced during the DLT observation period (cycle 1/day 1 through cycle 1/day 28) of the phase 1 portion of the study.

Guidelines for gilteritinib dose interruption and reduction for the phase 2 portion are provided in [Table 5].

The dose levels potentially used include the following [Table 4]:

Table 4 Gilteritinib Dose Levels

Dose Level (DL)	Gilteritinib Dose
DL - 0	120 mg ^a
DL - 1	80 mg
DL - 2	40 mg

^a Starting dose for gilteritinib

The gilteritinib dose may be initially reduced by 1 dose level per day. The gilteritinib dose can be further reduced by a second dose level if the subject has already experienced clinical benefit. Note that dose reductions should occur in a step-wise manner. Only 2 dose level reductions are permitted. Dose reduction can occur during the treatment cycle based on the dose reduction guideline in [Table 5]. Additionally, if the investigator deems it necessary to ensure subject safety, dosing may be interrupted or reduced for reasons other than those provided in [Table 5]. In the unusual circumstance that dosing is interrupted or reduced for reasons not specified in the tables, the investigator should promptly inform the study medical monitor or his/her designee. If the gilteritinib dose has been reduced for related toxicities, it cannot be re-escalated. Any subjects that have been off treatment for more than 14 days other

than for HSCT or a study drug related AE, may only resume treatment after discussion with the medical monitor.

Table 5 Guidelines for Gilteritinib Dose Interruption or Reduction Event

Gilteritinib Dosing Instructions	
Nonhematological Events	
Grade 3 toxicity at least possibly related to gilteritinib	Dosing will be interrupted for up to 14 days. If the AE resolves to \leq grade 1 within 14 days, the subject may resume dosing at the reduced dose.
Grade 4 toxicity at least possibly related to gilteritinib	Treatment will be discontinued.
QTcF > 500 ms	See [Section 5.4.4]
Myelosuppression	
Myelosuppression in the presence of CR, CRp or CRi	Dose may be reduced without interruption if the following criteria are met: Subject has received a minimum of 2 cycles of gilteritinib Platelets < $25 \times 10^9/L$ and/or absolute neutrophil count (ANC) $\leq 0.5 \times 10^9/L$ Marrow blasts < 5% No evidence of extramedullary disease Further dose reduction is permitted if dosing 1 full cycle at the reduced dose has not resulted in the desired hematologic recovery.

AE: adverse event; CR: complete remission; CRc: composite complete remission; CRi: complete remission with incomplete hematologic recovery; CRp: complete remission with incomplete platelet recovery; ECG: electrocardiogram; QTcF: Fridericia-corrected QT interval

5.1.3 Atezolizumab Dose Interruption

Refer to the following for atezolizumab dose modification recommendations:

Table 6 Recommended Dosage Modifications for Adverse Reactions (Atezolizumab)

Adverse Reaction	Severity of Adverse Reaction ^a	Dosage Modifications
Pneumonitis [see Warnings and Precautions (6.3) in the current IB]	Grade 2	Withhold dose until Grade 1 or resolved and corticosteroid dose is less than or equal to prednisone 10 mg per day (or equivalent)
	Grade 3 or 4	Permanently discontinue
Hepatitis [see Warnings and Precautions (6.3) in the current IB]	AST or ALT > 3 and ≤ 8 x ULN or total bilirubin > 1.5 and ≤ 3 x ULN	Withhold dose until Grade 1 or resolved and corticosteroid dose is less than or equal to prednisone 10 mg per day (or equivalent)
	AST or ALT > 8 x ULN or total bilirubin > 3 x ULN	Permanently discontinue
Colitis or diarrhea [see Warnings and Precautions (6.3) in the current IB.]	Grade 2 or 3	Withhold dose until Grade 1 or resolved and corticosteroid dose is less than or equal to prednisone 10 mg per day (or equivalent)
	Grade 4	Permanently discontinue
Endocrinopathies (including but not limited to hypophysitis, adrenal insufficiency, hyperthyroidism, and type 1 diabetes mellitus) [see Warnings and Precautions (6.3) in the current IB]	Grade 2, 3, or 4	Withhold dose until Grade 1 or resolved and clinically stable on hormone replacement therapy.

Table continued on next page

Adverse Reaction	Severity of Adverse Reaction ^a	Dosage Modifications
Other immune-mediated adverse reactions involving a major organ [see Warnings and Precautions (6.3) in the current IB]	Grade 3	Withhold dose until Grade 1 or resolved and corticosteroid dose is less than or equal to prednisone 10 mg per day (or equivalent)
	Grade 4	Permanently discontinue
Infections [see Warnings and Precautions (6.3) in the current IB]	Grade 3 or 4	Withhold dose until Grade 1 or resolved
Infusion-Related Reactions [see Warnings and Precautions (6.3) in the current IB]	Grade 1 or 2	Interrupt or slow the rate of infusion
	Grade 3 or 4	Permanently discontinue
Persistent Grade 2 or 3 adverse reaction (excluding endocrinopathies)	Grade 2 or 3 adverse reaction that does not recover to Grade 0 or 1 within 12 weeks after last TECENTRIQ dose	Permanently discontinue
Inability to taper corticosteroid	Inability to reduce to less than or equal to prednisone 10 mg per day (or equivalent) within 12 weeks after last TECENTRIQ dose	Permanently discontinue
Recurrent Grade 3 or 4 adverse reaction	Recurrent Grade 3 or 4 (severe or life-threatening) adverse reaction	Permanently discontinue
Previously experienced a skin adverse reaction on prior treatment with other immune-stimulatory anticancer agents	Grade 3 or 4 (severe or life-threatening reaction)	Caution when considering the use of atezolizumab
Suspected cutaneous adverse reactions	Grade 3 or 4	Refer to a dermatologist for further diagnosis and management
	SJS or TEN	Withhold dose until confirmation of diagnosis
Confirmed SJS or TEN	Any Grade	Permanently discontinue

SJS: Stevens-Johnson Syndrome; TEN: Toxic Epidermal Necrolysis

^a National Cancer Institute Common Terminology Criteria for Adverse Events (NCI CTCAE) version 4.0

Refer to the pharmacy manual or current IB for any updates.

5.1.3.1 Additional Dosing Interruption Guidelines

- Cycle 1: If the cycle 1/day 15 dose of atezolizumab is withheld due to, a treatment-related AE then the cycle 1/day 15 dose should be skipped and atezolizumab administration resumed at day 1 of the next cycle, if the treatment-related event has resolved or returned to grade 1.
- Subsequent cycles 2 and beyond: if the day 1 and/or day 15 dose of atezolizumab in a cycle is delayed due to a treatment-related AE, then atezolizumab administration should be skipped until the next scheduled atezolizumab dose (e.g., day 1 or day 15) of a cycle.

- In subsequent cycles, atezolizumab and gilteritinib may be interrupted for situations other than treatment related AEs such as medical/surgical events or logistical reasons not related to study therapy. Subjects should be placed back on study therapy within 14 days of the scheduled interruption, unless otherwise discussed with the medical monitor. The reason for interruption should be documented in the subject's study record.

5.1.4 Previous and Concomitant Treatment (Medication and Non-Medication Therapy)

All medications and concomitant treatments administered from 28 days prior to cycle 1/day 1 through the EOT Visit must be recorded in the electronic case report form (eCRF).

Concomitant medications should be collected for reported or ongoing AE/serious adverse events (SAEs) through 30 days after the last dose of study drug for subjects who have discontinued treatment. For subjects who undergo HSCT, concomitant medications should be collected for reported or ongoing AE/SAEs through start of conditioning treatment or 30 days after the last dose of study drug, whichever comes first. Treatment with concomitant drugs that are strong inducers of CYP3A are prohibited. Treatment with concomitant drugs that are strong inhibitors or inducers of P-gp and concomitant drugs that target serotonin 5HT_{2B}R or sigma nonspecific receptor are to be avoided with the exception of drugs that are considered absolutely essential for the care of the subject. Treatment with concomitant drugs that are strong inhibitors of CYP3A should be avoided with the exception of antibiotics, antifungals and antivirals that are used as standard of care to prevent or treat infections. If CYP3A inhibitors are used concomitantly, subjects should be closely monitored for AEs.

Precaution should be used in use of gilteritinib with concomitant drugs that are known to prolong QT or QTc intervals.

Precaution should be used in use of gilteritinib with concomitant drugs that are substrates of BCRP, since the transporter has been shown to be inhibited by gilteritinib in in vitro studies.

Common strong CYP3A inhibitors, strong CYP3A inducers, drugs targeting the serotonin receptor, P-gp inhibitors or inducers and drugs known to prolong QT or QTc intervals are listed in [[Appendix 12.4 List of Prohibited and/or Cautionary Concomitant Medications](#)]. The investigator should consult individual labels for all drugs that the subject is taking to evaluate if they fall into any of the above named categories. For concomitant drugs that have the potential to prolong QT or QTc intervals, a cardiology consult should be obtained as medically indicated. Any other treatments of AML (including but not limited to chemotherapy, radiotherapy, surgery, immunotherapy or cellular therapy) are prohibited during therapy with gilteritinib with the exception of hydroxyurea up to 5 g daily for up to 2 weeks to keep the absolute blast count below $50 \times 10^9/L$, prophylactic intrathecal chemotherapy or cranial irradiation. Participation in another interventional study while on treatment is prohibited.

Refer to [[Appendix 12.4 List of Prohibited and/or Cautionary Concomitant Medications](#)], as well as the country specific atezolizumab package insert for additional details on excluded or cautionary use of medications.

5.1.5 Treatment Compliance

Study subjects should be counseled on the need to meet 100% compliance with study drug. Investigator or designee should ensure that study subjects meet this goal throughout the study period. When study drug is administered at the research facility, it will be administered under the supervision of study personnel.

Compliance of gilteritinib will be monitored by the accounting of unused medication returned by the subject at visits and the subject diary. Compliance will be documented in EDC and IRT.

Reasons for dose reduction or interruption will also be recorded in the eCRF.

Treatment compliance should be monitored closely and deviation in compliance should be reported to the sponsor, except in cases where directed by protocol or principal investigator (e.g., account for dose interruptions, adjustments, etc.).

5.1.6 Criteria for Continuation of Treatment

Not applicable for this study.

5.1.7 Restrictions During the Study

See Inclusion/Exclusion Criteria in [Sections 3.2 and 3.3].

5.2 Demographics and Baseline Characteristics

5.2.1 Demographics

Demographic information will be collected for all subjects and will include age, sex, race and ethnicity.

5.2.2 Medical History

Medical history includes all significant medical conditions other than AML that have resolved prior to informed consent. Conditions that are ongoing at the time of consent will be collected as baseline conditions on the Medical History eCRF. Details that will be collected include the onset date, recovery date and CTCAE grade [National Cancer Institute, 2017], if applicable for ongoing conditions.

5.2.3 Diagnosis of the Target Disease, Severity, and Duration of Disease

5.2.3.1 Disease History

AML diagnosis and studies related to AML subtype classification will be collected and will include date, bone marrow evaluations, histopathology, cytogenetics, immunophenotyping and cytochemistry, lumbar puncture results if performed (RBCs, white blood cells with differential, cytospin results) and related genetic syndromes. Dates for diagnostic procedures will be collected.

5.2.3.2 FMS-like Tyrosine Kinase Mutation Status

All subjects must have documented FLT3 mutation by the local institution after completion of the subject's last interventional treatment.

Bone marrow/blood sampling, processing, storage and shipment instructions will be provided in the Laboratory Manual. Refer to the Laboratory Manual for more detailed information.

5.2.4 Performance Status

The ECOG Scale [Oken et al, 1982] will be used to assess performance status [Table 7] and will be obtained and recorded according to the Schedule of Assessments [Table 1].

Table 7 ECOG Performance Status

Grade	Description
0	Fully active, able to carry on all predisease performance without restriction.
1	Restricted in physically strenuous activity but ambulatory and able to carry out work of a light or sedentary nature, e.g., light house work, office work.
2	Ambulatory and capable of all self-care but unable to carry out any work activities. Up and about more than 50% of waking hours.
3	Capable of only limited self-care, confined to bed or chair more than 50% of waking hours.
4	Completely disabled. Cannot carry on any self-care. Totally confined to bed or chair.
5	Dead.

ECOG: Eastern Cooperative Oncology Group

5.3 Efficacy Assessments

5.3.1 Bone Marrow Aspirate and Biopsy

Bone marrow samples will be collected at screening, cycle 2/day 1 and cycle 3/day 1. For subjects who do not achieve a CR, CRp or CRi, the bone marrow assessments will be repeated on day 1 of every 2 subsequent cycles. For subjects who achieve a CRc (CR, CRp or CRi), bone marrow will be repeated 1 month after the date of remission and every 3 subsequent cycles or if there is suspicion of relapse in the whole blood. Bone marrow samples are also required at the EOT Visit and as clinically indicated. If bone marrow aspirate is unobtainable due to technical difficulties such as dry tap, a tube of whole blood (ethylenediaminetetraacetic acid [EDTA]) along with bone marrow biopsy should be collected instead. Remaining bone marrow aspirate and/or whole blood samples will be used for MRD analysis and may be used for other biomarker analyses in relation to treatment outcomes [described in Section 5.7] If bone marrow aspirate is unobtainable at relapse (e.g., dry tap), a peripheral blood smear should be collected along with bone marrow biopsy lab. All samples will be sent to the central lab. Refer to the laboratory manual for additional details.

5.3.2 Response Assessments

Response to treatment will be defined per modified Cheson criteria [Cheson et al, 2003] as outlined below for up to the end of 2 cycles and end of treatment.

5.3.2.1 Composite Complete Remission (CRc) rate

Defined as the rate of all complete and incomplete remission (i.e., CR+ CRp + CRi).

5.3.2.2 Complete Remission (CR)

For subjects to be classified as being in CR, they must have bone marrow regenerating normal hematopoietic cells and achieve a morphologic leukemia-free state and must have an absolute neutrophil count (ANC) $> 1 \times 10^9/L$ and platelet count $\geq 100 \times 10^9/L$, and normal marrow differential with $< 5\%$ blasts, and they must be red blood cell (RBC) and platelet transfusion independent (defined as 1 week without RBC transfusion and 1 week without platelet transfusion). There should be no evidence of extramedullary leukemia.

5.3.2.3 Complete Remission with Incomplete Platelet Recovery (CRp)

For subjects classified as being in CRp, they must achieve CR except for incomplete platelet recovery ($< 100 \times 10^9/L$).

5.3.2.4 Complete Remission with Incomplete Hematological Recovery (CRi)

For subjects to be classified as being in CRi, they must fulfill all the criteria for CR except for incomplete hematological recovery with residual neutropenia $< 1 \times 10^9/L$ with or without complete platelet recovery. RBC and platelet transfusion independence is not required.

5.3.2.5 Complete Remission with Partial Hematologic Recovery (CRh)

For subjects classified as being in CR, except if their ANC is $> 0.5 \times 10^9/L$ and their platelets are $> 50 \times 10^9/L$.

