6.1.3 Response Definition

Response to treatment will be defined per modified Cheson criteria [2003] as outlined below.

- Complete Remission (CR)

For subjects to be classified as being in CR, they must have bone marrow regenerating normal hematopoietic cells and achieve a morphologic leukemia-free state and must have an ANC $> 1 \times 10^9/L$ and platelet count $\geq 100 \times 10^9/L$, and normal marrow differential with $< 5\%$ blasts, and they must be red blood cell (RBC) and platelet transfusion independent (defined as 1 week without RBC transfusion and 1 week without platelet transfusion prior to disease assessment). There should be no evidence of extramedullary leukemia.

- Complete Remission with Incomplete Platelet Recovery (CRp)

For subjects classified as being in CRp, they must achieve CR except for incomplete platelet recovery ($< 100 \times 10^9/L$).

- Complete Remission with Incomplete Hematological Recovery (CRi)

For subjects to be classified as being in CRi, they must fulfill all the criteria for CR except for incomplete hematological recovery with residual neutropenia $< 1 \times 10^9/L$ with or without complete platelet recovery. RBC and platelet transfusion independence is not required.

- Composite Complete Remission (CRc)

For subjects to be classified as being in CRc at a post-baseline visit, they must either achieve CR, CRp or CRi at the visit.

- Complete Remission with Partial Hematological Recovery (CRh)

For subjects classified as being in CR, except if their ANC is $> 0.5 \text{ Gi/L}$ and their platelets are $> 50 \text{ Gi/L}$.

- Partial Remission (PR)

For subjects to be classified as being in PR, they must have bone marrow regenerating normal hematopoietic cells with evidence of peripheral recovery with no (or only a few regenerating $\leq 2\%$) circulating blasts and with a decrease of at least 50% in the percentage of blasts in the bone marrow aspirate/biopsy with the total marrow blasts between 5% and 25%.

- Relapse

Relapse after CR, CRp or CRi is defined as a reappearance of leukemic blasts in the peripheral blood or $\geq 5\%$ blasts in the bone marrow aspirate/biopsy not attributable to any other cause or reappearance or new appearance of extramedullary leukemia.

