7.4.2 Analysis of Secondary Efficacy Endpoint

CR rate, best response rate, duration of remission, OS and EFS will be summarized using descriptive statistics. The CR rate, best response rate with the corresponding 95% confidence interval will be reported. The survival curve and the median time for time to event variables will be estimated using the Kaplan-Meier method and will be reported along with the corresponding 95% confidence interval.

The SAS code used to produce median from Kaplan-Meier estimates and corresponding 95% CI will be similar to that shown below:

```
proc lifetest data=adtte plots=(s) outsurv=surv;  
time survtime*censor(0);
```

run;

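### CRh is defined by lower count limits only, so the rule as written takes in every CR or nobody; the CRh rate needs an explicit exclusion of CR

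*Protocol*

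**What the plan says.** Protocol 5.3.2.5 opens its definition of CRh with "For subjects classified as being in CR, except if their ANC is" and completes it with two floors: ANC above 0.5 and platelets above 50 × 10⁹/L. The synopsis has the same definition. SAP 6.1.3 repeats it with the same two numbers in Gi/L.

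CR (Protocol 5.3.2.2, SAP 6.1.3) requires ANC above 1 × 10⁹/L and "platelet count $\geq 100 \times 10^9/L$, and normal marrow differential with $< 5\%$ blasts", with transfusion independence and no extramedullary leukemia.

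The neighbouring categories each carry an upper limit. CRp (Protocol 5.3.2.3) is CR apart from platelets below 100 × 10⁹/L. CRi (Protocol 5.3.2.4) is CR apart from "incomplete hematological recovery with residual neutropenia $< 1 \times 10^9/L$ with or without complete platelet recovery".

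Protocol 2.3.2 and SAP 6.1.2 list CRh as a secondary endpoint. SAP 6.1.4 calculates the CRh rate in the same way as the CR rate: subjects with the response over the analysis population, with missing responses counted as non-responders. It also lists a duration of CR and, separately, a duration of CR/CRh. On analysis, SAP 7.4.2 says "CR rate, best response rate, duration of remission, OS and EFS will be summarized using descriptive statistics" and promises a 95% confidence interval for the CR and best response rates. Neither that section nor Protocol 7.4.1 names the CRh rate.

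**The concern.** CRh should describe subjects whose marrow is in remission but whose counts have recovered only in part. A definition with floors and no ceiling does not separate them from subjects whose counts have recovered fully. SAP 6.1.4 does not repair this, because it carries the response definition straight into a numerator with no rule that removes CRs.

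At stake is the numerator of a named secondary endpoint. Two programmers working from the same text could produce CRh rates that differ by the whole CR count, and a reader of the results table could not tell which derivation had been used.

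**Working it through.** The documents state no CRh figure to reproduce, so the check is one of set inclusion, followed by an illustration of size.

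**Inputs** (× 10⁹/L, all other CR criteria taken as met)

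| Category | ANC | Platelets | Source |
|---|---|---|---|
| CR | > 1 | ≥ 100 | Protocol 5.3.2.2 |
| CRp | > 1 | < 100 | Protocol 5.3.2.3 |
| CRi | < 1 | any | Protocol 5.3.2.4 |
| CRh | > 0.5 | > 50 | Protocol 5.3.2.5, SAP 6.1.3 |

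**Step 1: does CR lie inside CRh?** ANC > 1 implies ANC > 0.5, and platelets ≥ 100 implies platelets > 50. So every CR meets both CRh limits. A grid of ANC 0 to 3 in steps of 0.05 and platelets 0 to 200 in steps of 5 agrees:

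- CR cells: 40 ANC values × 21 platelet values = 840, and all 840 also meet the CRh limits.
- CRh cells in total: 50 × 30 = 1,500, so 1,500 − 840 = 660 meet CRh but not CR.
- Of those 660, 40 × 9 = 360 are also CRp, 9 × 30 = 270 are also CRi, and 30 (ANC exactly 1) are neither.

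**Step 2: which readings does the sentence allow?**

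| Reading | Who is CRh | What CR/CRh then means |
|---|---|---|
| CR criteria with the count limits lowered | every CR plus the partial recoveries | the same set as CRh |
| CR unless both limits are exceeded | nobody, since every CR exceeds both | the same set as CR |
| Short of CR on counts, but above the floors | partial recoveries only | a true union of two groups |

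Only the third reading gives the CR/CRh label in SAP 6.1.4 a meaning of its own. It is also the only one for which the text lacks the necessary words.

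**Step 3: size if CRs are included.** Let *h* be the subjects in CRh but not CR, *c* the subjects in CR, and *n* the denominator. The rate as written is (*h* + *c*)/*n*; the exclusive rate is *h*/*n*; the difference is *c*/*n*, the CR rate itself. The documents give no expected CR or CRh counts, so *h* = 5 and *c* = 5, 10 and 15 are assumed, with *n* = 49, the planned phase 2 maximum:

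| *c* (CR) | CRs included | CRs excluded |
|---|---|---|
| 5 | 10/49 = 20.4% | 5/49 = 10.2% |
| 10 | 15/49 = 30.6% | 5/49 = 10.2% |
| 15 | 20/49 = 40.8% | 5/49 = 10.2% |

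The Clopper-Pearson 95% interval for 5/49 is 3.4% to 22.2%. The inclusive rates in the last two rows lie outside it.

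**Step 4: what else uses CRh?** CRc is CR + CRp + CRi (Protocol 5.3.2.1), and best response is built from CR, CRp, CRi and PR (Protocol 5.3.2.9). Neither refers to CRh, so the primary endpoint, the Simon boundaries and the best response rate do not change.

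**The case against.** The best defence is that the intent is plain. 'Except' marks a shortfall in the CRp and CRi definitions, the endpoint's name says partial recovery, and the SAP treats CR/CRh as a combination. A sensible programmer would exclude CRs. This stands as evidence of intent, and it is why the inclusive reading should not be presented as the only one. It does not supply the missing limit: CRp and CRi state theirs and CRh does not.

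Two stronger readings are tempting, and the documents do not support them.

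- *That CRs will be counted twice in a CR + CRh rate.* Neither document forms such a rate by addition. CR/CRh appears only as a duration, over subjects in either category, and that set is the same whether CRh includes or excludes CR.
- *That CRh has been left out of the analysis.* SAP 6.1.2 lists the CRh rate, SAP 6.1.4 gives its calculation and missing-data rule, SAP 7.1 provides frequencies and percentages for categorical data, and duration of CR/CRh falls under duration of remission in SAP 7.4.2. What is absent is a named line and a stated confidence interval.

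It is also fair to object that 'does not meet CR' settles a single assessment only. Marrow is sampled at cycle 2/day 1 and cycle 3/day 1 (Protocol 5.3.1), so a subject could be CRh at the first and CR at the second and count in both rates. That is correct, and the fix has to cover it.

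**Conclusion.** The definition is wrong as written and should be corrected. Its limits admit every CR or, under the other literal reading, nobody; neither result matches the distinction that the SAP draws between CR and CR/CRh. If CRs are included, the CRh rate is overstated by exactly the CR rate. The percentages above rest on assumed counts and a full phase 2 of 49; that the excess equals the CR rate does not.

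The reach is limited to one descriptive secondary endpoint. The absence of a named CRh line and interval in the analysis sections is a minor gap in detail.

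**What to change.** 1. In the synopsis, Protocol 5.3.2.5 and SAP 6.1.3, define CRh as: *meets all CR criteria except that ANC is > 0.5 and platelets are > 50 × 10⁹/L, and does not meet CR (ANC ≤ 1 or platelets < 100 × 10⁹/L)*.
2. In SAP 6.1.4, state that the CRh rate counts subjects who reach CRh but not CR by the same time point; that CR/CRh is the subject-level union; and that CRh may overlap with CRp and CRi and does not enter CRc.
3. As a minor completion, name the CRh rate with its 95% CI in SAP 7.4.2 and Protocol 7.4.1.

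The cost is one sentence in each of three places, a short counting rule in the SAP and one table row. No data collection, sample size or decision rule changes.
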